# 6.3.3 Safety Analysis

Adverse events are not expected; however, all subjects entered into the study at Visit 1 will be included in the safety analysis. The frequencies of AEs by type, body system, severity and relationship to study drug will be summarized if at all present. SAEs (if any) will be described in detail.

AE incidence will be summarized along with the corresponding exact binomial 95% twosided confidence intervals.

#### 6.4 Sample Size and Power

For the principal endpoint, the tinnitus intensity scale ranges from 1-10. Assuming an average tinnitus intensity of 5 and a standard deviation of plus or minus 2 (such that 95% of the venous pulsatile tinnitus population has tinnitus intensity between 1 and 9). Intensity scale measurements will be averaged across individual submissions and across participants. With 16 paired evaluations per participant and 20 participants total, that creates 320 non collar tinnitus intensity measures.

Setting an alpha of p=.05 and a power of 0.8 (beta=0.2), we expect a minimum effect of a 1 point decrease between the no collar and collar measurements. To be conservative, we will preserve the 2 point standard deviation assumed for the baseline measure to apply to the collar relief measure. These parameters allow us to evaluate the viability of our sample size.

$$n_{g} \doteq (z_{lpha/2} + z_{eta})^{2} rac{\sigma_{1}^{2} + \sigma_{2}^{2}}{(\mu_{1} - \mu_{2})^{2}}$$

Where n is the number of analyses that will allow our minimum effect size to be significant Substitution lends us the following

 $\begin{array}{l} n_{\rm g} = (1.96 {+}~ 0.8416)^{2*} (2^2 {+} 2^2) / (2)^2 \\ n_{\rm g} = 15.86 \end{array}$ 

Not only is our overall study well in exceeding the number of intensity measurement differences needed to measure a significant effect; we will be able to assess the significant effect within each participant, given that each participant will complete both the with and without collar scales a total of 16 times. This gives our study strong internal and external validity.

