# 4.1.2 Between Visit (at home) phase

Patient wears collar for <4 hours total while awake for symptomatic relief as needed

Patient reports daily average tinnitus intensity with and without collar, length of use, and any adverse events through REDCAP email/text link

Continues daily for 14 days

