#### 6.3.2 Efficacy Analysis

The primary analysis will be based on an intention to treat approach and will include all subjects who complete the study.

The primary efficacy endpoint will be the change in tinnitus intensity with and without the collar, averaged within and across each patient's completion of the tinnitus scales. This means that there will be 16 paired collar and no collar measurements per patient, one at each clinic visit and one each day during the 14 day intervening period. The significance of this change will be evaluated using a unidirectional t-test.

Secondary endpoints will include the following:

- Temporality of symptom relief
  - Subjects with and without collar scores will be averaged for each day of the study, ANOVA testing will evaluate for the presence of a significant time component.
- Supervised vs. unsupervised use
  - The mean relief recorded at the first and second visit will be averaged and compared avross patients with the mean relief recorded during at home use using a bidirectional t test.
- QOL impacts
  - Evaluated for each scale using bidirectional t test

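### Section 6.4 states a 1-point minimum effect but calculates with 2 points, and it sets 320 repeated ratings against a two-group, two-sided formula that does not match the planned test

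*Combined protocol and SAP*

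**What the plan says.** Section 6.4 (Sample Size and Power) assumes a mean intensity of 5 on a 1–10 scale and an SD of 2, chosen so that "95% of the venous pulsatile tinnitus population has tinnitus intensity between 1 and 9". It sets alpha at 0.05 and power at 0.8, states that "we expect a minimum effect of a 1 point decrease between the no collar and collar measurements", and carries the SD of 2 over to the with-collar rating. The formula adds two variances and divides by the squared difference in means. The substituted line uses z-values of 1.96 and 0.8416, variances of 2² and 2², and a denominator of (2)². The printed result is 15.86.

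The section multiplies 20 participants by 16 evaluations to get 320 measures and draws three conclusions:

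- On overall size, the study is "well in exceeding the number of intensity measurement differences needed to measure a significant effect".
- On single participants, the section says "we will be able to assess the significant effect within each participant", because each participant completes both scales 16 times.
- On validity, it concludes: "This gives our study strong internal and external validity".

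On the analysis, section 6.3.2 says that "there will be 16 paired collar and no collar measurements per patient", averages them, and adds: "The significance of this change will be evaluated using a unidirectional t-test". The synopsis also specifies a one-sided test. Section 4.1.2 has the collar worn at home "while awake for symptomatic relief as needed".

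**The concern.** There are two separate defects.

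The first is the substitution. The effect stated in words is 1 point and the effect in the arithmetic is 2. The difference enters squared, so the required number changes by a factor of 4.

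The second is the unit and the test. The adequacy claim sets a count of repeated ratings against a requirement that assumes independent observations in two separate groups. The study has one cohort, each person is their own control, and the planned test is one-sided. The natural reading of section 6.3.2, though not spelled out there, is a paired test on one mean difference per participant, so n is 20.

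Section 6.4 is the only support for the sample size in the documents, and section 2 says the pilot data, if they show efficacy, will be used to apply for a multicenter grant. A reader cannot tell whether 20 participants were judged against 1 point or 2, and the section draws strong conclusions from the result.

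**Working it through.** **Inputs from section 6.4:** SD 2 with and without the collar, stated effect 1 point, substituted effect 2 points, z = 1.96 and 0.8416. **From section 6.3.2:** one-sided t-test, 16 pairs per patient, averaged. **Not in the documents:** the SD of the with/without difference (within a person or between participants' means), the correlation between the two ratings, and the correlation among one person's repeated differences.

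**1. Reproducing the printed figure.** n = (z_α/2 + z_β)² × (σ₁² + σ₂²) / (μ₁ − μ₂)², and (1.96 + 0.8416)² = 7.849.

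| Effect | Sides | Calculation | n |
|---|---|---|---|
| 2 points | two | 7.849 × 8 / 4 | 15.70 |
| 1 point | two | 7.849 × 8 / 1 | 62.8 |
| 1 point | one | (1.6449 + 0.8416)² × 8 / 1 | 49.5 |

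Only the 2-point, two-sided version comes near 15.86. The gap between 15.86 and 15.70 is a small slip, since both round up to 16. The gap between 15.86 and 62.8 is not.

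**2. The within-participant claim.** It rests on 16 pairs exceeding 15.86. At the stated effect, 16 is far short of 62.8 or 49.5. The plan's own formula with 16 gives 29% power two-sided, or 41% one-sided.

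Whether the claim holds in fact is unknown, because the SD of 2 describes spread across the population, not within one person. For a one-sided 0.05 paired t-test on 16 differences from one person (noncentral t, df 15, differences treated as independent), power for 1 point is:

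| Assumed within-person SD | 1.0 | 1.25 | 1.5 | 2.0 | 2.83 |
|---|---|---|---|---|---|
| Power | 98% | 92% | 82% | 60% | 38% |

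The SD must be about 1.53 or less for 80%. As-needed wear makes 16 a maximum. As an illustration only, 8 completed pairs would need an SD of about 1.02 or less.

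**3. The planned test.** One-sided 0.05 paired t-test on 20 participant mean differences (df 19):

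| Assumed SD of participant mean differences | Power, 1 point | Power, 2 points |
|---|---|---|
| 1.0 | over 99% | over 99% |
| 1.5 | 89% | over 99% |
| 2.0 | 70% | over 99% |
| 2.83 | 45% | 92% |

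80% power needs an SD of about 1.73 or less for 1 point, or about 3.47 or less for 2 points.

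The values 1.5, 2.0 and 2.83 correspond to SD = 2√(2(1 − r)) with r = 0.72, 0.5 and 0, if the plan's SD of 2 applied to participant means. On that footing an SD of 1.73 needs r of about 0.62.

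**4. What averaging could do.** If a single difference has SD s and one person's 16 differences have intraclass correlation ICC, the SD of a participant mean is s√((1 + 15·ICC)/16). Power for 1 point with 20 participants, all values assumed:

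| s | ICC 0.3 | ICC 0.5 | ICC 0.7 | ICC 1.0 |
|---|---|---|---|---|
| 2.0 | 98% | 91% | 82% | 70% |
| 2.83 | 83% | 67% | 56% | 45% |

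The 320 ratings count in full only at ICC 0. At ICC 0.5 the design effect is 1 + 15 × 0.5 = 8.5, and 320 / 8.5 is about 38.

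**The case against.** The strongest reply is that nothing here shows 20 participants to be too few. That is right. The 320 ratings exceed even 62.8, so the substitution error does not by itself overturn the overall claim. Two of the three mismatches with the planned test also work in the plan's favour: two-sided alpha asks for more than the one-sided test needs (62.8 against 49.5), and leaving out the covariance overstates the variance of the difference when the two ratings are positively correlated. Only counting repeated ratings as separate information flatters the study. The 70% and 45% figures apply the plan's rating SD with no gain from averaging, so they should not be headlined. A lower SD belongs in the range.

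It is also fair that section 6.4 takes 20 as given and uses the formula to check it, that it never uses the word independent, and that the within-participant claim is unsupported rather than disproved.

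None of this removes the contradiction. A check run at twice the stated effect does not check the stated effect, and comparing 320 with the required n makes sense only if the ratings carry independent information. Pilot status is no answer either, because the plan chose to state alpha, power and a minimum effect and to draw conclusions from them.

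**Conclusion.** The concern holds, and section 6.4 must be corrected. The printed requirement of 15.86 belongs to a 2-point effect. At the stated 1 point it is 62.8, four times as large, or 49.5 one-sided, about three times. The within-participant claim fails on the plan's own inputs. The overall adequacy claim rests on a count of repeated ratings and on a formula for a different test.

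Whether 20 participants give 80% power for 1 point cannot be determined from the documents. Over assumed SDs of 1.0 to 2.83 for the participant mean differences, power runs from over 99% to 45%. If 2 points was intended, it is 92% or more over the same range. These figures assume a paired test on one mean difference per participant, which is the natural reading of section 6.3.2. No loss of power has been shown. What is wrong is the stated figure and the claims built on it.

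**What to change.** Keep the 20 participants, the endpoint and the test, and change section 6.4 only.

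1. Reconcile the 1-point effect in the text with the 2 in the substitution, and say which was intended.
2. Replace the formula and its result with power for the planned test. For example: *With 20 participants and a one-sided 0.05 paired t-test on each participant's mean difference, power for a 1-point decrease is over 99%, 89%, 70% or 45% if the SD of those mean differences is 1.0, 1.5, 2.0 or 2.83 (assumed values). An SD of about 1.73 or less gives 80% power. Each mean uses at most 16 pairs, because collar use at home depends on need.* If 2 points was intended, the matching figures are over 99% at the first three SDs and 92% at 2.83, with 80% power at an SD of about 3.47 or less.
3. Delete the within-participant claim, the claim that the number of measurements well exceeds the need, and the sentence on internal and external validity.

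The cost is rewording, with no extra patients. The drawback is that, at 1 point, the statement becomes less favourable, and the plan must say openly that power depends on an SD it does not yet know.

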# 3.2.2 Total Number of Study Sites/Total Number of Subjects Projected

The study will be conducted at approximately 1 investigative site in the United States. This site is the UNC Meadowmont ENT outpatient clinic.

Recruitment will stop when approximately 20 subjects are recruited. It is expected that approximately 22 subjects will be enrolled to produce 20 evaluable subjects.

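### Section 6.4 claims a significant effect can be assessed within each participant from 16 pairs, but the design does not support individual-level significance

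*Combined protocol and SAP*

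**What the plan says.** Section 6.3.2 (Efficacy Analysis) defines the data for each person: "This means that there will be 16 paired collar and no collar measurements per patient, one at each clinic visit and one each day" of the home period. The primary analysis averages these within and across patients and applies one test: "The significance of this change will be evaluated using a unidirectional t-test". The other listed analyses are an ANOVA for time, a two-sided comparison of supervised with home use, and a two-sided t test for each quality-of-life scale. No test per participant is listed.

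Section 6.4 (Sample Size and Power) states "Setting an alpha of p=.05 and a power of 0.8 (beta=0.2") and an effect size: "we expect a minimum effect of a 1 point decrease between the no collar and collar measurements". It assumes an SD of 2 without the collar and keeps it for the other measure: "we will preserve the 2 point standard deviation assumed for the baseline measure to apply to the collar relief measure". It then derives a required number of 15.86. From this it argues that the study as a whole has more than enough measurements and, further, that "we will be able to assess the significant effect within each participant, given that each participant will complete both the with and without collar scales", since each participant does so 16 times. The next sentence concludes that the study is strong in both internal and external validity.

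Section 3.2.2 gives the number of people: "It is expected that approximately 22 subjects will be enrolled to produce 20 evaluable subjects".

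**The concern.** The sentence in 6.4 treats each participant as a small trial that can reach significance alone. Neither 6.3.2 nor 6.4 gives a test, sidedness, significance level, responder definition, allowance for repeated daily ratings or multiplicity rule for that purpose. The only significance level stated is .05.

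Two things follow if someone acts on the sentence. With about 20 people tested separately, some may come out significant by chance and be reported as people in whom the collar works. With only 16 pairs each, many people with a real effect of the size the plan names would be missed. A count of significant participants would then be hard to interpret in either direction. Section 2 says the pilot data, if they show efficacy, will support a multicenter grant application, so such a count could carry weight.

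**Working it through.** **Inputs.** From 6.4: level .05, power 0.80, SD 2 per condition, difference 1 point in the text and 2 in the substitution, normal quantiles 1.96 and 0.8416. From 6.3.2: 16 pairs per person, one-sided primary test. From 3.2.2: 20 evaluable participants, about 22 enrolled. Not in the documents, and therefore assumed: the correlation between a person's with-collar and without-collar scores, and the correlation between that person's differences on successive days.

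**1. The plan's own figure.** The formula in 6.4 is n = (1.96 + 0.8416)² × (2² + 2²) / difference².
- Difference 2, as substituted: 7.849 × 8 / 4 = 15.70. The plan prints 15.86, about 1% higher, so the figure reproduces closely enough.
- Difference 1, as stated in the text: 7.849 × 8 / 1 = 62.8, or 63.

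The apparent sufficiency of 16 pairs per person therefore comes from the 2-point substitution. At the stated 1 point the same formula asks for about four times as many.

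**2. False positives if each person were tested.** Different participants give independent tests, so with no collar effect P(at least one) = 1 − (1 − a)^k.

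| Level per person, benefit direction | k = 20 | k = 22 | Expected number, k = 20 |
|---|---|---|---|
| .05 (one-sided, as for the primary test) | 1 − 0.95²⁰ = 64.2% | 67.6% | 1.0 |
| .025 (from the 1.96 in 6.4) | 1 − 0.975²⁰ = 39.7% | 42.7% | 0.5 |

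The chance passes one half when the per-person error exceeds 1 − 0.5^(1/20) = 3.4%.

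**3. Correlated days.** The rows above assume that a person's 16 differences are independent. To see how far this matters, 200,000 null series of 16 differences with first-order autoregressive correlation were simulated and tested with an ordinary one-sample t test.

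| Assumed lag-1 correlation | Per-person error at nominal .025 / .05 | At least one of 20 |
|---|---|---|
| 0.1 | 3.7% / 6.7% | 53% / 75% |
| 0.3 | 7.2% / 11.2% | 78% / 91% |
| 0.5 | 12.7% / 17.1% | 93% / 98% |

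The documents give no value for this correlation. The table shows sensitivity, not an expected rate.

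**4. Power within one person.** With 16 pairs and a 1-point effect, the noncentrality is (1 / SD of the difference) × √16, on 15 degrees of freedom.
- SD 2 per condition, uncorrelated: SD of the difference = √(4 + 4) = 2.83 and noncentrality 1.41. Power is 38% one-sided and 26% two-sided at .05.
- If the SD of 2 is read as that of the difference itself: noncentrality 2.00. Power is 60% one-sided and 46% two-sided.

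Both readings fall short of 80%. For comparison, a 2-point effect with SD of the difference 2.83 gives 85% one-sided and 75% two-sided, so the individual-level claim comes near its target only at an effect twice the one stated.

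**The case against.** The best defence is that 6.4 describes a capability, not an analysis. Person-level testing is absent from the objectives (2.1, 2.2), the endpoints (6.1, 6.2), the efficacy measures (5.2) and the analyses (6.3.2), and no responder rule exists. Section 10 also says that data will be published only in aggregate. Most of this stands. A reader might infer that the plan schedules about 20 unadjusted tests, or that the trial's main error rate is inflated; the documents support neither. The false-positive figures apply only if such tests are run and read one by one, and the primary test's type I error is untouched.

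A reader might also infer that a false individual responder is more likely than not. That holds at one-sided .05 with independent differences, but not at the .025 implied by the 1.96 in 6.4, where the figure is about 40%. The plan fixes neither level nor sidedness for such tests. Rates above 80% appear only with assumed day-to-day correlation. Taking the difference between two scores from the same day may remove some shared fluctuation, so correlation in the raw scores would not settle the value.

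What the defence does not remove is that 6.4 rests a validity claim on this capability. Aggregate publication does not prevent a statement that so many of 20 participants improved significantly. The shortfall in step 4 also needs no assumption that the tests are planned: it contradicts the stated capability directly, at the plan's own effect size.

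**Conclusion.** The point holds as a defect in what 6.4 says the study can conclude, not as a fault in the primary analysis. If individual tests were run without adjustment, the chance of at least one false-positive participant with no collar effect would be about 40% to 64% for 20 people and independent daily differences, depending on which of the plan's two levels is used. It would be higher with positive serial correlation (53% to 75% at an assumed 0.1). Independently of that, the sentence borrows its support from a 2-point substitution. At the stated 1 point, within-person power is 26% to 38% with uncorrelated conditions, and at most 60% on the more favourable reading of the SD. The change is worth making because it limits what may be claimed from the pilot and is nearly free.

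**What to change.** In 6.4, replace the within-participant sentence with: *Each participant's mean relief will be displayed descriptively with an interval; no significance claim will be made for individual participants.* Delete the following sentence on validity, which depends on it. Reconcile the 1-point effect in the text with the 2 in the substitution, and recompute the required number accordingly. State one sidedness for both 6.3.2 and 6.4.

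A mixed model with a random collar effect would be a reasonable way to describe variation between people, but it is optional in a pilot of this size. Multiplicity control is needed only if person-level significance claims are kept. In that case 6.3.2 should name the test, its sidedness, how serial correlation is handled and the adjustment; for example, Holm across 20 people starts at .05/20 = .0025, which would lower the already low individual power further.

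The cost is a few sentences of protocol text, with no new data or participants. The study gives up the claim of individual-level significance.

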#### 6.5 Interim Analysis

Not planned. Significant safety adverse events would lead to termination of study.

# 7 STUDY DEVICE (STUDY DEVICE OR OTHER STUDY INTERVENTION)

# 7.1 Description

# 7.1.1 Usage

The collar can be worn while awake for no more than 4 hours daily by participants who meet the inclusion/exclusion criteria. This point shall be educated to participants who enroll.

#### 7.1.2 Treatment Compliance and Adherence

The daily scales completed by participants during the at home period will contain reminders of the safety and adherence stipulations of the collar

# 7.1.3 Safety

Subject safety will be monitored by observation and intervention of adverse events during the physician-supervised fitting period at the beginning of the study and by education of the participants to discontinue use of the collar with any significant change in physical wellbeing or onset of new symptoms and immediate reporting of that occurrence to the PI and Faculty Advisor through the REDCAP link.

#### 8 SAFETY MANAGEMENT

#### 8.1 Clinical Adverse Events

Clinical adverse events (AEs) will be monitored throughout the study.

#### 8.2 Adverse Event Reporting

Since the study procedures are not greater than minimal risk, SAEs are not expected. If any unanticipated problems related to the research involving risks to subjects or others happen during the course of this study (including SAEs) they will be reported to the IRB in accordance with CHOP IRB SOP 408: Unanticipated Problems Involving Risks to Subjects. AEs that do not meet prompt reporting requirements will be summarized in narrative or other format and submitted to the IRB at the time of continuing review (if continuing reviews are required), or will be tracked and documented internally by the study team but not submitted to the IRB (if continuing reviews are not required).

#### 9 STUDY ADMINISTRATION

# 9.1 Treatment Assignment Methods

There will be no randomization or blinding of participants.

#### 9.2 Data Collection and Management

All data will be collected and stored in a password-protected redcap database available only to access by study personnel. All study personnel are trained and certified in HIPAA. Data collection will occur through individualized links to REDCAP database administered on secure clinic iPad during visits or sent to participant phone/email during home phase.

#### 9.3 Confidentiality

All data and records generated during this study will be kept confidential in accordance with Institutional policies and HIPAA on subject privacy. Data and records will not be used for any purpose other than conducting the study. All data and records will be stored in password protected REDCAP database.

No identifiable data will be used for future study without first obtaining IRB approval or determination of exemption.

